10.4. Managing Hyperglycemia Risks in Diabetic Subjects

Although hyperglycemia is not anticipated as a consequence of the device, some subjects may develop uncontrolled hyperglycemia in the course of the study (e.g., as a result of progression of their diabetes or an intercurrent illness). Signs or symptoms of acute metabolic deterioration, or presence of serious intercurrent illness or trauma should lead to prompt subject evaluation. Responses may include close follow up, adjustment of anti-diabetic medication or diet, or hospitalization. Subjects who require insulin treatment for greater than 14 consecutive days should terminate study participation and have the study device removed.

10.5. Early Device Removal

Early device removal should be considered in the following situations:

- Subject experiences abdominal pain and the pain does not resolve in 5-7 days, in combination with ulcer observation
- Subject has signs of ulcer progression:
 - Enlargement of peptic ulcer by greater than or equal to 25% in length or width over 8 weeks and with a minimum width (short axis) of 1 cm
 - Bleeding, Hgb drops ≥ 2 g/dL
 - Developing upper abdominal pain, which does not resolve on medical therapy
- Subject has an ulcer size of ≥ 2 cm in diameter or width (the smaller measurement between the length and width), OR ≥ 3 cm x 1cm not responding to medication
- Subject requires insulin treatment for greater than 14 consecutive days
- Subject loses $\geq 20\%$ of his/her total body weight in any four-week post-placement period
- Subject achieves a BMI of ≤ 22 kg/m² for two consecutive visits before the 12-months follow up
- Subject becomes pregnant

Device removal should be performed according to the device removal procedure described in Section 11.9.10.1 and in the IFU.

To ensure that both study groups are treated the same in a sham-controlled study, the control subjects will be treated as if he/she has received the device. For example, if a control subject has lost $\geq 20\%$ of his/her total body weight in any four-week period during follow up, the subject will exit the study as if he/she will have the device removed.

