10.2. Managing Endoscopic Observations

Tissue effects such as erythema, erosions, or ulcers may be observed during endoscopic surveillance. Limited clinical experience to date suggests that some patients may be asymptomatic while others may develop symptoms.

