10.2.2. Guidelines for Managing Endoscopic Observations

The following algorithm (

Figure 13) is suggested for managing endoscopic observations in subjects after the index procedure.

Figure 13. 

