11.4. Biochemical Measurements

Fasting blood samples will be obtained at the screening and baseline visits, and at the 6- and 12-month follow-up visits. The following analyses will be performed:

- CBC (Complete blood count), including differential (screen and baseline visits only)
- Chemistry Panel 20 (screen and baseline visits only)
- Lipid levels and lipoproteins (triglycerides, LDL-C, HDL-C, and total cholesterol)
- Glucose, insulin, HbA1c
- High sensitivity C-reactive protein

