11.9.2. Baseline Visit (Within One Week Prior to the Index Procedure)

The following evaluations/procedures are to be performed within 7 days prior to the index procedure:

- Abbreviated physical examination including vital signs (temperature, systolic/diastolic blood pressure, respiration rate, heart rate)
- Body mass assessment (body weight, calculation of BMI, and measurement of circumferences)
- Concomitant medications
- IWQOL-Lite assessment
- Eating Inventory assessment
- Visual Analog Scale assessment
- Urine pregnancy test for females capable of becoming pregnant
- Blood tests
 - CBC with differential
 - Chemistry panel 20
 - Lipid levels and lipoproteins,
 - Glucose, insulin, HbA1c, high sensitivity C-reactive protein
- Assessment for eligibility
- Brief lifestyle counseling according to Appendix C, including recommendation and instruction to follow the caloric target of 1200-1500 kcal/day for subjects ≤ 114 kg (≤ 250 lb) and 1500-1800 kcal/day for subjects > 114 kg (> 250 lb)

If the subject is no longer eligible for the study due to a change in the subject's condition, such as pregnancy, abnormal blood test values, or weight change resulting in a BMI outside of the protocol range, the subject will be excluded from the study and documented as a screen failure.

This visit is not required in subjects whose screening visits and tests are performed within 7 days of the index procedure. In this case, data collected from the screening visit will serve as baseline data.

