11.9.8. Six-Month Post-Index Procedure (180 ± 14 Days)

The following data are to be collected:

- Abbreviated physical examination (temperature, systolic/diastolic blood pressure, respiration rate, heart rate)
- Body mass assessment (body weight, calculation of BMI, and measurement of circumferences)
- Concomitant medications
- IWQOL-Lite
- Visual Analog Scale assessment
- Eating Inventory assessment
- Blood tests (lipid levels and lipoproteins, glucose, insulin, HbA1c, high sensitivity C-reactive protein)

- Assessment of AEs that occurred since the last visit
- Brief lifestyle counseling

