11.9.11. Unscheduled Visit

If a subject is hospitalized, seen in the emergency room, or has an unscheduled clinic visit, efforts should be made to collect the following data:

- Relevant medical history, physical examination, and laboratory testing findings
- Concomitant medications
- Assessment of AEs

These assessments should be documented on the eCRFs as appropriate.

11.9.12. Telephone Contact at Months 7 (210±7 days), 8 (240±7 days), 10 (300±7 days), and 11 (330-14 days)

In Months 7, 8, 10, and 11, subjects will be contacted by telephone by study personnel(s) who deliver(s) the lifestyle interventions. The subject and study personnel will have a brief (15-minute) telephone calls. During these calls, subjects will report on changes in weight, dietary intake, eating behavior, and physical activity level. These telephone calls are designed to promote adherence to the lifestyle modification protocol. The provider will reinforce positive behaviors consistent with the lifestyle modification program and problem solve issues related to weight gain, increased caloric intake or decreases in physical activity.

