APPENDIX B: SCHEDULE OF EVENTS

Evaluation	Visit	Screen	Baseline	Index Procedure	1wk	1M	2M	4M	6M	7M	8M	9M	10M	11M	12M
	Days	Within 56 days	Within 7 days	Day 0	D7 ±2	D30 ±7	D60 ±14	D120 ±14	D180 ±14	D210 ±7	D240 ±7	D270 ±21	D300 ±7	D330 -14	D365 ±30
Informed consent		X													
Patient demographics		X													
Medical history		X													
Current medication		X	X	X	X	X	X	X	X			X			X
Psychological evaluation		X													
Inclusion criteria		X	X												
Exclusion criteria (general)		X	X												
Exclusion criteria (endoscopic)				X											
Lifestyle counseling			X		X	X	X	X	X			X			X
Follow up telephone call										X	X		X	X	
Height		X													
Weight		X	X	X	X	X	X	X	X			X			X
BMI		X	X	X	X	X	X	X	X			X			X
Body circumference		X	X	X	X	X	X	X	X			X			X
Physical exam		X	X ¹	X ¹	X ¹	X ¹	X ¹	X ¹	X ¹			X ¹			X
EKG		X													
CBC w/differential		X	X												
Chemistry panel 20		X	X												
Blood tests ²		X	X						X						X
Urine pregnancy test		X	X												
Stool H pylori test		X													
Patient Health Questionnaire		X													
IWQOL-Lite			X						X						X
Satiety Assessments (VAS & Eating Inventory)			X		X	X			X						X
Adverse event assessment				X	X	X	X	X	X			X			X
Blinding assessment					X										X
Device removal															X
Study exit															X

1 – Abbreviated physical: temperature, systolic/diastolic blood pressure, respiration rate, heart rate

2 -- Blood tests include lipid panel, fasting blood glucose, insulin, HbA1c, C - reactive protein

3 – For Treatment group only

APPENDIX C: LIFESTYLE MODIFICATIONS PROGRAM...REDACTED

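### No haemoglobin is scheduled after device placement, although section 10.5 uses a fall of 2 g/dL as a sign for considering early removal

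*Combined protocol and SAP*

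**What the plan says.** Section 10.5 gives situations in which early device removal should be considered. One is ulcer progression, and its signs include "Bleeding, Hgb drops" of 2 g/dL or more. The same section says Control subjects are to be handled as though they carried the device.

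Section 11.4 lists the laboratory tests. The entry for the blood count reads "CBC (Complete blood count), including differential (screen and baseline visits only"; the chemistry panel has the same restriction. The 6-month visit (11.9.8) lists "Blood tests (lipid levels and lipoproteins, glucose, insulin, HbA1c, high sensitivity C-reactive protein", and 11.9.10 lists the same panel at 12 months. Appendix B marks the blood count only at screening and baseline, and its footnote 2 says "Blood tests include lipid panel, fasting blood glucose, insulin, HbA1c, C - reactive protein".

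Three other provisions bear on the point:

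- Section 10.2, on tissue effects such as erosions and ulcers, notes that "some patients may be asymptomatic while others may develop symptoms".
- Section 11.9.11 asks sites to collect, at unscheduled visits and hospital contacts, "Relevant medical history, physical examination, and laboratory testing findings". It names no specific test.
- Section 10.2.2 refers to an algorithm (Figure 13) that "is suggested for managing endoscopic observations in subjects after the index procedure". The figure is redacted.

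**The concern.** The plan sets a numerical haemoglobin threshold for a decision about the device but schedules no measurement that would show when a subject crosses it. HbA1c, which is in the follow-up panel, is not a haemoglobin concentration and cannot stand in for it.

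The risk is one the plan recognises. Section 3.5.2 lists ulceration and bleeding among the anticipated events. Residence here is 12 months with the third-generation device, whereas the feasibility study (3.4.3) followed 20 subjects with the second-generation device for 3 or 6 months. That study reported no bleeding, but it covers at most half of the residence time now planned.

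Two things are at stake. Blood loss that raises no suspicion is never checked against the 2 g/dL figure. And because the visible safety analysis (15.5.5) summarises adverse events only, a fall that nobody measured cannot appear in it, so the sham arm cannot be used to judge whether haemoglobin falls more with the device.

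**Working it through.** The plan gives no figure of its own for this point. The check is a count of scheduled values, date arithmetic on the visit windows, and the cost and yield of the remedy.

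**1. Scheduled haemoglobin values.** From 11.4, the visit lists 11.9.1 to 11.9.10 and Appendix B:

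- Before placement: 2 (screening and baseline). This becomes 1 where the separate baseline visit is not needed, because then "data collected from the screening visit will serve as baseline data" (11.9.2).
- After placement: 0.

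**2. Time without a scheduled value.** Inputs: the 6-month visit at day 180 ± 14 (11.9.8); the 12-month visit and removal at day 365 ± 30 (11.9.10, 11.9.10.1); baseline within 7 days before placement (11.9.2).

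| Stretch | Nominal (days) | Range from windows (days) |
|---|---|---|
| Now: placement to removal | 365 | 365 − 30 = 335 to 365 + 30 = 395 |
| With fix: placement to 6-month draw | 180 | 180 − 14 = 166 to 180 + 14 = 194 |
| With fix: 6-month to 12-month draw | 365 − 180 = 185 | 335 − 194 = 141 to 395 − 166 = 229 |

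Measured from the last scheduled blood count, the present stretch can reach 395 + 7 = 402 days. With the fix, baseline to the 6-month draw is at most 194 + 7 = 201 days. The longest nominal stretch after placement falls from 365 to 185 days, roughly half.

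**3. What each added value can do.** The 6-month value can inform early removal, and it coincides with a scheduled endoscopy (11.9.3 schedules these at 2, 6 and 12 months). The 12-month value falls in the planned removal window, so it serves only the safety summary and follow-up at exit.

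**4. Cost.** 270 subjects × 2 draws = 540 assays at most.

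**5. Incidental falls and precision.** The documents give no SD for change in haemoglobin. Assume the change from baseline is normal with mean 0 and SD between 0.6 and 1.0 g/dL. The probability of a fall of at least 2 g/dL is then Φ(−2/SD). The 95% half-width for the between-arm difference in mean change is 1.96 × SD × √(1/n_T + 1/n_C). The group sizes are from 15.4: 180 and 90 as enrolled, 162 and 81 after the allowance for losses.

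| Assumed SD (g/dL) | Expected falls, 270 subjects | Of which 90 Control | Half-width, 180 v 90 | Half-width, 162 v 81 |
|---|---|---|---|---|
| 0.6 | 0.12 | 0.04 | 0.15 | 0.16 |
| 0.8 | 1.68 | 0.56 | 0.20 | 0.21 |
| 1.0 | 6.14 | 2.05 | 0.25 | 0.27 |

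For example, at SD 1.0, Φ(−2) = 0.02275 and 270 × 0.02275 = 6.14. The half-width is 1.96 × 1.0 × √(1/180 + 1/90) = 1.96 × 0.1291 = 0.25 g/dL.

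**The case against.** The strongest reply is that the plan contains no contradiction. The haemoglobin fall in 10.5 sits under ulcer progression and prompts consideration, not mandatory removal. It is a rule for a subject who already has an ulcer and is bleeding, and for such a subject a pre-placement value exists and a test can be ordered. The redacted Figure 13 may already require one, and redacted sections 5.4 and 15.5.6 may also bear on this. Silent lesions are sought directly by endoscopy at 2, 6 and 12 months. Recognised bleeding or anaemia is an adverse event, assessed at every visit and summarised under 15.5.5, and the safety objective (15.3.2) asks for no more. The remedy yields one value that can affect removal, at a visit that already has an endoscopy, and nothing in the documents says how many true cases it would find.

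Much of this stands. For-cause use is possible, the benefit cannot be quantified, and the gap is limited to unsuspected loss and missing comparative data. Three parts do not stand:

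- Redaction cannot explain the schedule, because the limit in 11.4 is explicit and visible. Anything in Figure 13 would follow a finding and would not be a scheduled value.
- Endoscopy shows lesions on the day. It does not measure cumulative blood loss, and none is listed between months 6 and 12.
- The other safeguards are partial. Section 9.1.2 allows aspirin 81 mg/day with a PPI. The anaemia exclusion admits women at 11.0 and men at 12.0 g/dL, from which a fall of 2 g/dL leads to 9.0 and 10.0 g/dL.

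**Conclusion.** The concern holds. The plan uses a 2 g/dL fall as a sign for considering removal and schedules no haemoglobin after placement, over a nominal 365 days (335 to 395 with the window). The consequence is limited to safety monitoring and safety description: silent blood loss may go unchecked, and the arms cannot be compared on haemoglobin. Neither co-primary endpoint is touched.

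The remedy is cheap and worth making, but modest. It leaves nominal stretches of 180 and 185 days without a value, and only the 6-month value can inform removal. The count of scheduled values and the intervals rest on the documents alone. The estimates of incidental falls and of precision rest on the assumed SD of 0.6 to 1.0 g/dL and a mean change of zero. Whether ulcer-triggered testing is already required depends on redacted text.

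**What to change.** - In 11.4, 11.9.8, 11.9.10 and Appendix B, add haemoglobin (or the full blood count) to the existing 6- and 12-month draws in both arms. Testing both arms fits the rule in 10.5 on handling Control subjects and protects the blind.
- State that a 6-month fall of at least 2 g/dL from baseline prompts clinical evaluation for bleeding, not automatic removal. Where screening serves as baseline, the screening value is the reference.
- In 15.5.5, add a descriptive summary by arm of change in haemoglobin from baseline at 6 and 12 months. No test is needed.
- If Figure 13 does not already require it, state in 10.5 that haemoglobin is measured whenever an ulcer or suspected bleeding is found.

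The cost is one assay at two visits that already draw blood, with no new visit or needle stick. The downside is the follow-up of incidental falls: about 0 to 6 subjects at 6 months under the assumption above, of whom about 0 to 2 would be sham subjects. A further value at the 2-month endoscopy visit would narrow the gap more but needs a new blood draw, so it is not part of this request.

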7.5. Patient Discontinuation

Once enrolled, each subject will remain in the study until the required follow-up period is complete. However, the subject has the right to withdraw from the study at any time without penalty or loss of benefit. The following events will result in terminating the subject's follow-up:

- Subject voluntary withdrawal
- Subject withdrawn by the Investigator as clinically indicated
- Subject becomes pregnant
- Subject lost to follow-up
- Subject death
- Study is terminated according to Section 5.6 (Early Study Termination)

In the case of subject withdrawal from the study, the TPS must be removed before the subject exits the study.

In case the TPS is removed early as described in Section 10.5, the subject's participation in the study is considered terminated. Any Adverse Events will be followed until resolution or stabilization according to Section 12.1.

In case a subject achieves normal BMI (≤ 22 kg/m²) for two consecutive visits before the 12-month follow up, the subject is considered to have completed the study. Subject will exit the study and the device should be removed in the treatment subjects.

A final endoscopy should be performed whenever possible before the Treatment subject exits the study.

The Sponsor must be notified of the reason for subject discontinuation. The site will document this information on the electronic case report form (eCRF) and make every effort to give a full description of the reason for withdrawal. Investigators must also report this information to the local IRB as defined by their institution's procedure.

Subjects who are terminated early will not be replaced by enrolling additional subjects.

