11.9.1. Screening Visit (Within 8 Weeks Prior to the Index Procedure)

At the screening visit, the following procedures/assessments will be performed to determine subject eligibility:

- Informed consent prior to the conduct of any study-related procedures
- Demographics (ethnicity, age, gender, education, marital status)
- Medical history, especially the assessment of risk factors and morbidities related to obesity and age when subject first noticed obesity
- Concomitant medications
- Physical examination
- Body mass assessment (body weight, height, calculation of BMI, and measurement of circumferences)
- Patient Health Questionnaire (PHQ-9)
- Behavioral evaluation by registered dietitian, behavioral specialist, or mental health professional
- Urine pregnancy test for females capable of becoming pregnant
- Stool test for *H. pylori*
- Blood tests
 - CBC with differential
 - Chemistry panel 20
 - Fasting lipid panel
 - Fasting blood glucose, insulin, HbA1c, C-reactive protein
- EKG
- Assessment of enrollment eligibility (inclusion/general exclusion criteria)

Each subject will be assessed for suitability to participate in the study by the site Investigator.

Subjects who meet all the inclusion criteria but none of the exclusion criteria will be scheduled for a baseline visit.

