Before the subject is discharged, s/he is to be provided with a subject information card. This card provides the phone number and name of the person to contact in case s/he needs medical attention related to the therapy. Additionally, the subject can provide this card to an emergency room doctor, allowing them to contact the Primary Investigator and obtain information about the study. A sample of the card is provided in Appendix G.

The subject should be placed on a liquid diet for 3 days, followed by soft food for a week, slowly returning to normal food in 10 days.

The following procedures/assessments will be performed during this visit:

- Abbreviated physical examination including vital signs (temperature, systolic/diastolic blood pressure, respiration rate, heart rate)
- Body mass assessment (body weight, calculation of BMI, and measurement of circumferences)
- Assessment of medications
- Endoscopic assessment
- Confirmation of eligibility
- TPS placement procedure

- Assessment of AEs that occurred during the procedure

Post-Procedure Follow-Up Visits

Post-procedure follow-up visits are summarized in Appendix B. They include:

- Office visits at 1 week, and 1, 2, 4, 6, 9, 12 months
- Endoscopic assessments at 2, 6, and 12 months
- Visual Analog Scale assessment at 1 week and 1, 6, and 12 month(s)
- Eating Inventory assessment at 1 week and 1, 6 and 12 month(s)
- Blood tests at 6 and 12 months
- IWQOL-Lite at 6 and 12 months
- Device removal at 12 months
- AE assessments at each follow-up visit
- Brief lifestyle counseling at each follow-up visit and brief telephone calls at 7, 8, 10, and 11 months.

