11.9.10.1. TPS Device Removal

The TPS is to be removed 365 ± 30 days after the index procedure under general or MAC anesthesia. An endoscopic assessment will be performed in all subjects followed by TPS removal in the Treatment group. The device removal procedure is described in detail in the IFU 

Subjects will be discharged according to the hospital and physician's discharge criteria.

All procedure- and device-related AEs must be followed until resolution or stabilization (the Investigator does not expect any further improvement or worsening of the event). Following study exit, follow-up will be according to clinical practice.

Subjects will be informed that his/her participation in this study is complete. The subject's study exit will be documented.

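### Pregnancy ends follow-up and is a listed situation for device removal, but no pregnancy test is listed after baseline, leaving 335 to 402 days untested up to the 12-month removal

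*Combined protocol and SAP*

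**What the plan says.** Section 7.5 introduces its list with "The following events will result in terminating" and goes on to the subject's follow-up; pregnancy is on that list. Section 10.5 includes "Subject becomes pregnant" among the situations in which early removal should be considered.

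Testing is listed at two points. The screening list (11.9.1, up to 8 weeks before the index procedure) and the baseline list (11.9.2, within 7 days before it) both contain "Urine pregnancy test for females capable of becoming pregnant". If screening itself falls in the last week, only one test is done: "This visit is not required in subjects whose screening visits and tests are performed within 7 days of the index procedure". A pregnancy found at baseline is a screen failure (11.9.2). In Appendix B the row "Urine pregnancy test" is readable and is marked under Screen and Baseline only.

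Procedures continue after placement. Section 11.9.3 lists "Endoscopic assessments at 2, 6, and 12 months", and section 11.9.10.1 states: "The TPS is to be removed 365 ± 30 days after the index procedure under general or MAC anesthesia". No visible list for the index procedure, the follow-up visits, unscheduled visits or telephone contacts contains a pregnancy test.

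The other visible safeguards are the birth-control commitment for the duration of participation (7.2), the exclusion of pregnancy planned in the next 12 months (7.3), the review of medical conditions at each visit (11.2) and the adverse event assessment at each follow-up visit.

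**The concern.** The protocol attaches consequences to pregnancy but, once the device is in place, lists no test to find it. Before placement it is stricter: a screening result may be up to 56 days old, so the test is repeated within 7 days of the procedure. The same caution is not applied to the following year, nor to the endoscopies and the removal under anesthesia within it.

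Several other situations in section 10.5 are looked for on schedule: weight and BMI at every office visit, ulcers at endoscopy, insulin use through medication review. Pregnancy depends on the subject knowing of it and reporting it. Two features could make that less reliable:

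- Nausea and vomiting are anticipated device effects (3.5.2), so early pregnancy symptoms could be put down to the device.
- Section 3.5.5 says the device's effect on absorption of oral medication is unknown, and 3.5.2 lists altered absorption as an anticipated event. If the agreed contraceptive is oral, the main safeguard might itself be affected. The protocol does not say which methods are used, so this is only a possibility.

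At stake is an unrecognised pregnancy continuing with the device in place, on a prescribed 1200 to 1800 kcal/day (8.1), through an endoscopy or a removal under anesthesia. The SAE definition (12.1.1) includes fetal distress, fetal death and congenital abnormality. The effect on %TBL is small: pregnancy ends follow-up, and the missing 12-month weight is imputed (15.5.3).

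**Working it through.** The plan states no figure for the untested interval, so there is none to reproduce. The check is date arithmetic on the windows in section 11.9 and Appendix B.

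**Inputs (days relative to the index procedure)**

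| Time point | Window |
|---|---|
| Last listed test (baseline, or screening if baseline is waived) | −7 to 0 |
| 2 months, 60 ± 14 | 46 to 74 |
| 6 months, 180 ± 14 | 166 to 194 |
| 12 months and removal, 365 ± 30 | 335 to 395 |

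**Interval as written (last test to 12-month removal)**

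- Shortest: 335 − 0 = 335 days.
- Longest: 395 + 7 = 402 days.

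Waiving the baseline visit does not change this, because the screening test must then lie within the same 7 days. The interval applies to subjects who reach month 12; an earlier exit shortens it.

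**Intervals with tests added at 2, 6 and 12 months**

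| Interval | Shortest | Longest |
|---|---|---|
| Baseline to 2 months | 46 − 0 = 46 | 74 + 7 = 81 |
| 2 to 6 months | 166 − 74 = 92 | 194 − 46 = 148 |
| 6 to 12 months | 335 − 194 = 141 | 395 − 166 = 229 |

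The longest untested interval for any subject is then 141 to 229 days; with visits on their target days it is 365 − 180 = 185.

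**Number of added tests**

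- Ceiling, if every subject were a woman of childbearing potential: 3 × 270 = 810.
- With 90% women (18/20 in ENDObesity I, section 3.4.3) and an assumed 50% to 80% of them of childbearing potential: 810 × 0.9 × 0.5 ≈ 365 to 810 × 0.9 × 0.8 ≈ 583.
- Allowing for the small feasibility sample (exact 95% CI for 18/20: 0.683 to 0.988): 810 × 0.683 × 0.5 ≈ 277 to 810 × 0.988 × 0.8 ≈ 640.

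The 50% to 80% share is an assumption; the documents do not give it. They also give no pregnancy rate, so the number of unrecognised pregnancies cannot be estimated.

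**The case against.** The strongest reply has four parts.

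1. **A positive test may change little.** Pregnancy already leads towards device removal, which is itself done under anesthesia, and at 12 months the device must come out anyway. This stands in part: the test does not avoid the procedure. It does let the investigator plan its timing and anesthesia, it ends the reduced-calorie prescription, and it sets 7.5 and 10.5 in motion. At 2 and 6 months it can do so long before the scheduled removal.

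2. **The year is not without surveillance.** There are seven office visits and four telephone contacts, with conditions and adverse events reviewed at visits, on top of the contraception commitment. This is true and lowers the risk. None of it is a test, and it finds mainly pregnancies that the subject already knows about.

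3. **The visible text is incomplete.** Endoscopic follow-up is redacted in the protocol summary, the removal section breaks off after pointing to the IFU, and the IFU is not available. A check before anesthesia may exist there or in local practice. This limits confidence about the procedures more than about the routine schedule, since the pregnancy-test row in Appendix B is itself readable. A check left to site practice is also not a requirement across up to 12 sites.

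4. **Test frequency is a judgment.** Sections 7.5 and 10.5 do not contradict Appendix B, and the harm is not quantified. Both statements are correct. The case rests on the protocol's own practice before placement and on the low cost of extending it.

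**Conclusion.** The concern holds. Following the visible plan, a woman of childbearing potential who completes the study has no scheduled pregnancy test for 335 to 402 days while pregnancy would end her follow-up and call for removal to be considered. That interval takes in the endoscopies at 2 and 6 months and runs up to the 12-month removal.

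It is a patient-safety weakness in the design. It has no bearing on type I error or power. The interval follows directly from the visit windows. The conclusion assumes that no test is required in the redacted text or the IFU. Confidence is moderate for that reason, and because the frequency of the harm is unknown.

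**What to change.** Extend the existing pregnancy-test row in Appendix B to the 2-, 6- and 12-month visits for women of childbearing potential, and add the matching bullet to sections 11.9.6, 11.9.8 and 11.9.10. Test both arms, which protects the masking and agrees with the rule in 10.5 that controls are handled as if they had the device. Require the result before any endoscopy or device removal at that visit. The handling of a positive result can stay as 7.5 and 10.5 have it.

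Intervals of about four months (2 to 6) and six months (6 to 12) would remain. The main gain is a check before each scheduled procedure.

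The cost is one schedule row, three bullets and at most 810 urine tests, more plausibly about 365 to 583 under the assumptions above. No extra visit, staff or invasive procedure is needed.
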